13.1. DERIVATIONS

Duration of exposure (days) = date of last study medication administration – date of first study medication administration + 1.

14. STUDY MEDICATION COMPLIANCE

Compliance will be presented for the Safety and ITT populations by treatment group, and overall, both continuously (mean percentage) and categorically (compliant vs. non-compliant, non-compliant <75% and non-

Document: K:\DSP\SM-13496\KVA95374\Biostatistics\Documentation\SAP

Author:

Version Number:

1.0

Version Date:

30MAR2017

Template No: CS_TP_BS016 – Revision 3

Reference: CS_WI_BS005

Effective Date: 01May2012

Copyright © 2012 [REDACTED] All rights reserved.

The contents of this document are confidential and proprietary to [REDACTED]. Unauthorized use, disclosure or reproduction is strictly prohibited.

complaint >125%, and patients with any missing compliance).

14.1. DERIVATIONS

At each visit, prior to dispensing study medication, previously dispensed study medication will be retrieved and assessed by tablet count. Compliance in the double-blind phase will be calculated overall as follows:

- Percent compliance = (number of tablets taken / number of tablets should have taken) x 100.
- Number of tablets taken = number of tablets dispensed – number of tablets returned. Lost tablets are considered to have been returned for the purpose of calculating compliance.
- Number of tablets should have taken = (number of tablets supposed to take in a day) x (number of exposure days).

If the number of tablets returned is missing, compliance will be missing. Non-compliance is defined as less than 75% or more than 125% non-missing overall compliance with the study medication. Patients with missing compliance are not classified as non-compliant, and are not considered to be protocol deviators.

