5.2. PER PROTOCOL POPULATION [PP]

The PP population will consist of patients from the ITT population who fulfill the following conditions:

- Patients who fulfill the inclusion criteria (3) to (7), and (10) (see Protocol Section 4.1.1) and do not meet any of the exclusion criteria (1), (5) to (12), (18) to (21), and (28) (see Protocol Section 4.1.2)
- Patients who have been treated for 14 days or longer
- Patients who receive 75% to 125% of study treatment in the treatment phase

Document: K:\DSP\SM-13496\KVA95374\Biostatistics\Documentation\SAP

Author: [REDACTED]

Version Number:

1.0

Version Date:

30MAR2017

Template No: CS_TP_BS016 – Revision 3

Reference: CS_WI_BS005

Effective Date: 01May2012

Copyright © 2012 [REDACTED] All rights reserved.

The contents of this document are confidential and proprietary to [REDACTED]. Unauthorized use, disclosure or reproduction is strictly prohibited.

- Patients who do not receive any psychotropic medication other than antiparkinson drugs, anxiolytics, and hypnotics during the treatment phase
- Patients who have no important protocol deviations as determined by a blinded data review

The first 3 conditions will be verified using SAS programming. A medical review will be conducted by [REDACTED] or Sponsor Medical team to identify psychotropic medications. A review sheet will be provided for identifying medications and the completed sheet will be incorporated into SAS derived datasets.

For identifying other important protocol deviations, a blind data review meeting will be convened with representatives from [REDACTED] and the Sponsor to determine whether the deviations require the patient to be removed from the PP population.

For analyses and displays based on PP, patients will be classified according to randomized treatment.

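### The missing-compliance exemption in SAP 14.1 conflicts with the 75% to 125% per-protocol condition and could retain patients whose counted cards already show under-dosing

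*SAP*

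**What the plan says.** SAP 14.1 works with a single figure for the whole treatment phase: "Compliance in the double-blind phase will be calculated overall as follows". Its numerator is a difference: "Number of tablets taken = number of tablets dispensed – number of tablets returned". The denominator is the daily tablet number times the days of exposure. Three rules follow.

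- Recorded losses: "Lost tablets are considered to have been returned for the purpose of calculating compliance". They therefore count as not taken, and compliance can still be computed.
- Absent counts: "If the number of tablets returned is missing, compliance will be missing".
- Classification: "Non-compliance is defined as less than 75% or more than 125% non-missing overall compliance with the study medication". The next sentence is the exemption: "Patients with missing compliance are not classified as non-compliant, and are not considered to be protocol deviators".

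SAP 14 also shows "patients with any missing compliance" as a category of its own. There is no rule for using the cards that do have a count.

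The PP definition in SAP 5.2 includes "Patients who receive 75% to 125% of study treatment in the treatment phase". Protocol 9.2.2 has the same condition. SAP 5.2 says this condition is checked by program. SAP 9 refers to section 5.2 for what a protocol violation is. SAP 3.3 reports no change from the analysis planned in the protocol.

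**The concern.** A PP population is meant to show the effect in patients dosed broadly as planned. Here the dosing condition is stated positively in one section, and another section excuses patients for whom it was not evaluated. An absent count is foreseeable: SAP 13 says repeatedly that the exposure and dose summaries do not depend on the card having been returned.

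The exemption also discards information. A patient may have five counted cards showing clear under-dosing, and one absent count removes that evidence from the classification. The treatment of losses runs the other way: a patient who reports lost cards is charged with all of their tablets, while a patient with no count at all is excused.

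At stake is how the PP analyses can be read: the MMRM and the LOCF ANCOVA on MADRS (protocol 9.5.2; SAP 15.1.4.1 and 15.1.4.4) and the repeat for CGI-BP-S (SAP 15.2.3.1). If the set may include demonstrably under-dosed patients, agreement between ITT and PP says less than it appears to.

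**Working it through.** The plan gives no figure for uncounted cards or for missing compliance, so there is none to reproduce. The packaging figures agree with each other: 6 columns × 9 rows = 54 tablets per card, which equals 6 tablets × (7 + 2) days.

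**Inputs**
- 54 tablets per card (protocol 5.1.2.1) and 6 tablets per day (protocol 5.2.3).
- Six scheduled cards, dispensed at Visits 2 to 7 (protocol 5.2.2).
- Limits of 75% and 125% (SAP 5.2 and 14.1).
- At least 14 days of treatment for PP (SAP 5.2).

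**Two steps of reading**
1. *One uncounted card makes the overall figure missing.* The numerator is one sum over the treatment phase, so one absent term leaves it undefined. No partial rule is given, and SAP 14 has a category for any missing compliance. This is the natural reading, but the text does not spell it out.
2. *Missing compliance leaves the patient in PP.* SAP 5.2 leaves the dosing check to a program, and 14.1 is the only text that tells the program how to treat a missing value. SAP 9 ties violations to 5.2, so being declared not a deviator carries over to PP. This too is an inference.

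**Bounds for 42 days with one of six cards uncounted**

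Tablets due = 6 × 42 = 252, and 75% of that is 189. Let *c* be the tablets taken from the five counted cards, on which 5 × 42 = 210 were scheduled.

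- Lowest possible compliance = *c* / 252 (nothing taken from the uncounted card).
- Highest possible compliance = (*c* + 54) / 252 (every tablet taken).

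The patient is certainly below 75% when *c* + 54 < 189, that is *c* ≤ 134, or 63.8% of 210. At *c* = 134 the maximum is 188/252 = 74.6%. If the uncounted card is credited with only its 7 scheduled days (42 tablets), the cut rises to *c* ≤ 146, or 69.5%.

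| Taken on counted cards | *c* | Lowest | Highest |
|---|---|---|---|
| 40% | 84 | 33.3% | 54.8% |
| 50% | 105 | 41.7% | 63.1% |
| 60% | 126 | 50.0% | 71.4% |
| 70% | 147 | 58.3% | 79.8% |

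The first three rows are below 75% whatever happened to the sixth card. The fourth cannot be decided. At *c* = 189 (90%) the lowest value is already 75.0%, so such a patient meets the lower limit for certain. The undecidable band is *c* = 135 to 188.

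**Shorter exposures, one card uncounted and credited with 54 tablets**

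| Days | Due | 75% | Scheduled on counted cards | Certainly <75% if taken ≤ |
|---|---|---|---|---|
| 14 | 84 | 63 | 42 | 8 |
| 21 | 126 | 94.5 | 84 | 40 |
| 28 | 168 | 126 | 126 | 71 |
| 35 | 210 | 157.5 | 168 | 103 |
| 42 | 252 | 189 | 210 | 134 |

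The case can therefore arise throughout the range of exposures that PP admits.

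**Contrast with recorded losses at 42 days, otherwise perfect dosing**
- One lost card: (252 − 42)/252 = 83.3%, compliant.
- Two lost cards: (252 − 84)/252 = 66.7%, non-compliant.

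The second patient is non-compliant, while the 40% patient above, with a maximum of 54.8%, is not.

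**The case against.** The strongest reply is that 14.1 never says such patients meet the PP condition. It governs compliance displays for the Safety and ITT populations. PP membership is set by 5.2, which is worded positively, so a program could treat a missing value as not meeting it. That is a fair reading, but it does not remove the conflict: 14.1 also says these patients are not deviators, and two programmers could build different PP sets from the same text.

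There are safeguards. Compliance is checked at Visits 3 to 8, and noncompliance is a listed reason for discontinuation (protocol 5.2.3 and 4.3.1). Missing data are queried, and all cards are to come back by the end of the study (protocol 8.5.1 and 5.1.4), so a card left at home may still be counted. Populations are agreed before unblinding (SAP 5), and SAP 14 makes missing compliance visible. These steps should reduce the number of uncounted cards. They do not say how to classify the patients who remain, and the exemption may limit what the blinded review of other important deviations can do about them.

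A reader might infer that any unreturned or lost card exempts a patient. The documents do not support that: recorded losses count as returned and are handled strictly. A reader might also infer that the PP estimate is diluted. Dilution is possible, and it would work against showing superiority, but nothing in the documents shows that it occurs. Many patients with one uncounted card would be undecidable or clearly adequate, not provably under-dosed.

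**Conclusion.** The concern holds as a conflict between SAP 14.1 and the PP condition in SAP 5.2 and protocol 9.2.2. If 14.1 governs, the plan can retain patients whose own counts place them below 75%: for 42 days and one uncounted card, those with 134 or fewer of 210 tablets taken on the other five.

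This rests on four assumptions: one absent count voids the overall figure; the exemption carries through to PP; the absent card was not recorded as lost; and only the six scheduled cards were dispensed. The first two are strong inferences, not explicit text.

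The consequence is limited. The number affected is not given. The primary MMRM in the ITT population does not use compliance. The PP analyses are supportive and stand beside the ITT LOCF ANCOVA, the random-effects pattern-mixture model and the placebo-based imputation. It would go too far to say that the PP population is known to contain under-dosed patients or that the primary conclusion is at risk. The change is worth making because the counts are already collected and the rule can be settled before unblinding.

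**What to change.** In SAP 14.1, replace the blanket exemption with a rule based on bounds.

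1. For each uncounted card, compute overall compliance once with 0 tablets and once with all 54 credited. Keep the present rule for recorded losses, and say explicitly that missingness is judged card by card.
2. If the highest value is below 75%, or the lowest is above 125%, classify the patient as non-compliant and exclude from PP.
3. If the whole range lies within 75% to 125%, classify the patient as compliant.
4. Report everyone else as indeterminate, including patients with no counts at all, and refer them to the blinded data review before unblinding. State the decision rule for them in SAP 5.2, so that 5.2 and 14.1 agree.

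Bounds are preferable to a ratio from the counted cards alone, which assumes that the uncounted card resembles the others. At 76% on five cards and nothing on the sixth, true compliance is 0.76 × 210/252 = 63.3%, yet the ratio would retain the patient. At 74% with all 54 taken, it is (0.74 × 210 + 54)/252 = 83.1%, yet the ratio would exclude the patient.

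The cost is a few sentences, a small programming change, some extra cases for the blinded review, and possibly a slightly smaller PP population.

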15. EFFICACY OUTCOMES

15.1. PRIMARY EFFICACY

15.1.1. PRIMARY EFFICACY VARIABLE & DERIVATION

The primary efficacy variable is the change from baseline in the MADRS total score at Week 6 for testing superiority of SM-13496 (20-60 or 80-120 mg/day) to placebo. The rater-administered MADRS data will be used for all statistical analyses. The full data for the questionnaire is collected on the eCRF.

The total score is calculated as the sum of all the component scores of the MADRS scale. The MADRS total score ranges from 0 to 60. Higher scores are associated with greater severity of Bipolar I disorder.

The change from baseline at week 6 is calculated as MADRS total score at week 6 minus the MADRS total score at baseline. This value will be a negative value if the patient condition has improved.

15.1.2. MISSING DATA METHODS FOR PRIMARY EFFICACY VARIABLE(S)

In the event that any component element of a total score is missing, then the total score will be set to missing.

Missing data at a visit will be accounted for using a combination of approaches. The MMRM method being used for the primary analysis includes an assumption that data is missing at random.

The primary analysis will also have a sensitivity analysis conducted using a LOCF variable which will impute a missing week 6 endpoint value.

Additionally, 2 sensitivity analyses will be conducted investigating alternate assumptions about missing data. For full information about these please see section 15.1.4.

Document: K:\DSP\SM-13496\KVA95374\Biostatistics\Documentation\SAP

Author: [REDACTED]

Version Number:

1.0

Version Date:

30MAR2017

Template No: CS_TP_BS016 – Revision 3

Reference: CS_WI_BS005

Effective Date: 01May2012

Copyright © 2012 [REDACTED] All rights reserved.

The contents of this document are confidential and proprietary to [REDACTED]. Unauthorized use, disclosure or reproduction is strictly prohibited.

15.1.3. PRIMARY ANALYSIS OF PRIMARY EFFICACY VARIABLE(S)

15.1.3.1. Montgomery-Asberg Depression Rating Scale (MADRS)

The primary efficacy variable is the change from baseline in the MADRS total score at Week 6 for testing superiority of SM-13496 (20-60 or 80-120 mg/day) to placebo, versus the null hypothesis of no difference versus placebo. The hypothesis for each SM-13496 treatment group will be considered independently.

Let μ_{20-60} , μ_{80-120} , and μ_{placebo} represent the mean changes from baseline in the MADRS total score at Week 6 in the 20-60mg, 80-120mg, and placebo groups, respectively. The following 2 hypotheses will be tested to compare the mean changes at Week 6 of each SM-13496 group with that of the placebo group:

- H01: $\mu_{20-60} = \mu_{\text{placebo}}$ versus the alternate H11: $\mu_{20-60} \neq \mu_{\text{placebo}}$.
- H02: $\mu_{80-120} = \mu_{\text{placebo}}$ versus the alternate H12: $\mu_{80-120} \neq \mu_{\text{placebo}}$.

The rater-administered MADRS data will be used for all statistical analyses.

The MMRM method will be used in the ITT population. The MMRM model will include treatment as a categorical factor, visit (Week 1, 2, 3, 4, 5, and 6; as a categorical variable), pooled center, the MADRS total score at baseline as a covariate, and the treatment-by-visit interaction. An unstructured covariance matrix will be used for the within-patient correlation and the Kenward-Rogers approximation will be used to calculate the denominator degree of freedom. In the case of a convergence problem with the unstructured covariance matrix, the following structures with robust sandwich estimator for the standard error of the fixed effect estimates will be assessed in a sequential fashion: heterogeneous Toeplitz, heterogeneous first-order autoregressive, and Toeplitz. Among these 3 covariance structures, the first structure yielding convergence will be used for the MMRM analysis. P-values for comparisons of primary efficacy variable at Week 6 between SM-13496 groups and the placebo group will be adjusted for multiplicity using a Hochberg procedure (section 7.4).

Effect size at Week 6 will also be presented and will be derived as the absolute value of the LS mean difference between the treatment groups divided by the model estimate of the standard deviation. To calculate the standard deviation of change from baseline at Week 6 based on MMRM model, the square root of the variance estimate for that visit, obtained from the SAS-estimated R matrix will be taken (O'Kelly & Ratitch, 2014). The variance estimates for the visits are obtained differently dependent upon the covariance structure being applied for the model. If the MMRM converges using the planned unstructured covariance structure then the diagonal of the R matrix will be used for variance estimate at each visit. In the case of non-convergence and the use of a heterogeneous Toeplitz based MMRM or first order auto-regressive MMRM then the diagonal cell corresponding to Week 6 from the R matrix can still be used to estimate the variance. However, in the case of non-convergence and the use of a regular Toeplitz based MMRM, the diagonal from the first column of the R matrix can be used as the variance estimate.

The mean change from baseline in the MADRS total score will be plotted by visit of discontinuation to assess whether there are dropout patterns that appear to violate the missing at random (MAR) assumption, which the MMRM is based upon.

Document:	K:\DSP\SM-13496\KVA95374\Biostatistics\Documentation\SAP	Version Number:	1.0
Author:	[REDACTED]	Version Date:	30MAR2017

Template No: CS_TP_BS016 – Revision 3
Effective Date: 01May2012

Reference: CS_WI_BS005

Copyright © 2012 [REDACTED] All rights reserved. [REDACTED] Unauthorized use, disclosure or reproduction is strictly prohibited.

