3.5 Sample size

The target number of the randomized patients is 501 (ie, 167 patients per treatment group)

Rationale

The sample size for the study has been determined by a Monte-Carlo simulation using the Statistical Analysis Software (SAS Version 9.2, SAS Institute). The sample size calculation is based on the number of patients required for the primary analysis in the intention-to-treat (ITT) population, where the primary analysis is performed on the change from baseline in the MADRS total score at Week 6. Hochberg procedure will

be utilized for the multiplicity adjustment to the multiple comparisons between each SM-13496 (20-60 and 80-120 mg/day) group and the placebo group.

A common effect size of 0.35 (ie, an intergroup difference in change from baseline of 3.5 with a standard deviation of 10) in the MADRS total score for both SM-13496 groups over placebo group was used for estimating the sample size. A sample size of 161 per group for a total of 483 patients was estimated to yield a complete power (probability of rejecting 2 null hypotheses) of 80%, with a one-sided 2.5% significance level using Hochberg procedure for multiplicity adjustment. Considering the possibility of patients who are randomized but who do not provide any post-baseline MADRS total score, the total sample size will therefore be 501 patients or 167 patients per treatment group.

The assumed effect size of 0.35 has been determined based on the PREVAIL 2 study of which study design is similar to that of the present study. In the PREVAIL 2 study, the sample size had been calculated with effect sizes of 0.39 for both SM-13496 groups (20-60 and 80-120 mg/day), and as a result, effect sizes were 0.45 for both SM-13496 groups over the placebo group on the change from baseline at Week 6 (last observation carried forward [LOCF]) in the MADRS total score. The result of the PREVAIL 2 study is shown in Table 2.

Table 2 Change from baseline in the MADRS total score at Week 6 (LOCF) – Analysis of Covariance –, Intention-to-Treat population, in the PREVAIL 2 study

	SM-13496 20-60 mg/day (N=161)	SM-13496 80-120 mg/day (N=162)	Placebo (N=162)
LS mean (SE)	-13.9 (0.80)	-13.9 (0.78)	-9.5 (0.79)
Inter-treatment difference vs. placebo (SE)	-4.5 (1.10)	-4.4 (1.10)	
Effect size	0.45	0.45	

LS means are from an analysis of covariance (ANCOVA) with treatment and pooled study site as fixed factors and baseline value as a covariate.

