9.5.2 Primary analysis

The primary efficacy variable is the change from baseline in the MADRS total score at Week 6 for testing superiority of SM-13496 (20-60 or 80-120 mg/day) to placebo.

The rater-administered MADRS data will be used for all statistical analyses. The MMRM method will be used in the ITT population. The MMRM model will include treatment as a categorical factor, visit (Week 1, 2, 3, 4, 5, and 6; as a categorical variable), pooled center, the MADRS total score at baseline as a covariate, and the treatment-by-visit interaction. An unstructured covariance matrix will be used for the within-patient correlation and the Kenward-Rogers approximation will be used to calculate the denominator degree of freedom. In the case of a convergence problem with the unstructured covariance matrix, the following structures with robust sandwich estimator for the standard error of the fixed effect estimates will be assessed in a sequential fashion: heterogeneous Toeplitz, heterogeneous first-order autoregressive, and Toeplitz. Among these 3 covariance structures, the first structure yielding convergence will be used for the MMRM analysis. P-values for comparisons of primary efficacy variable at Week 6 between SM-13496 groups and the placebo group will be adjusted for multiplicity using a Hochberg procedure.

A sensitivity analysis for the primary efficacy variable will be performed using an analysis of covariance (ANCOVA) model on the ITT population. The response variable for the model will be the change from baseline in the MADRS total score at Week 6 (LOCF). The ANCOVA model will include treatment as a categorical factor, pooled study site and the MADRS total score at baseline as a covariate. The MMRM and LOCF ANCOVA analysis will also be performed on the PP population to obtain additional information on the robustness of results.

The mean change from baseline in the MADRS total score will be plotted by visit of discontinuation to assess whether there are dropout patterns that appear to violate the missing at random (MAR) assumption, which the MMRM is based upon.

Study sites with small number of patients will be pooled for the analyses. The strategy for pooling sites will be provided in the statistical analysis plan.

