APPENDIX 3. SAS CODE

Treatment: TRTPN
Analysis visit: AVISIT

1. Mixed Model Repeated Measures (MMRM) Analysis

Note: Ensure that input dataset is sorted by USUBJID AVISIT prior to initiating the MIXED procedure.

```
ods output estimates=outset /*Output from estimate statement*/  
diffs=outdiff /*Treatment Group Comparison*/  
R=outr /*R matrix */  
lsmeans=outlsmean; /*LSmeans of each treatment group*/
```

```
PROC MIXED;  
CLASS SUBJID POOLSITE TRTPN AVISIT;  
MODEL CFB = BASE POOLSITE TRTPN AVISIT TRTPN*AVISIT/DDFM=KR;  
REPEATED AVISIT /TYPE=UN SUBJECT=SUBJID R;  
LSMEANS TRTPN* AVISIT /PDIFF CL;  
ESTIMATE 'LINEAR TREND TEST FOR DOSE RESPONSE'  
TRTPN 0 1 -1 TRTPN*AVISIT 0 0 0 0 0 0 0 0 0 0 0 0 0 1  
0 0 0 0 0 0 -1/CL;  
ESTIMATE 'DOSE-RESPONSE 20-60 vs 80-120' TRTPN -1 1 0 TRTPN*AVISIT  
0 0 0 0 0 0 -1 0 0 0 0 0 0 1 0 0 0 0 0 0 0/CL;  
RUN;
```

a. Mixed Model Repeated Measures (MMRM) Analysis for the case above
model fails to converge

```
PROC MIXED empirical;
```

Document:	K:\DSP\SM-13496\KVA95374\Biostatistics\Documentation\SAP	Version Number:	1.0
Author:	[REDACTED]	Version Date:	30MAR2017

Template No: CS_TP_BS016 – Revision 3
Effective Date: 01May2012

Reference: CS_WI_BS005

Copyright © 2012 [REDACTED] All rights reserved.
The contents of this document are confidential and proprietary to [REDACTED]. Unauthorized use, disclosure or reproduction is strictly prohibited.

```
CLASS SUBJID POOLSITE TRTPN AVISIT;  
MODEL TOTCFB = TOTBL POOLSITE TRTPN AVISIT TRTPN*AVISIT;  
REPEATED AVISIT /TYPE=XXX SUBJECT=SUBJID R;  
LSMEANS TRTPN*AVISIT /PDIFF CL;  
ESTIMATE 'LINEAR TREND TEST FOR DOSE RESPONSE'  
TRTPN 0 1 -1 TRTPN*AVISIT 0 0 0 0 0 0 0 0 0 0 0 0 1  
0 0 0 0 0 0 -1/CL;  
ESTIMATE 'DOSE-RESPONSE 20 vs 80-160' TRTPN -1 1 0 TRTPN*  
AVISIT 0 0 0 0 0 0 -1 0 0 0 0 0 0 1 0 0 0 0 0 0/CL;  
RUN;
```

XXX: application order
Heterogeneous Toeplitz (TYPE=TOEPH)
Heterogeneous first-order autoregressive (TYPE=ARH(1))
Toeplitz (TYPE=TOEP)

2. Analysis of Covariance

```
PROC MIXED;  
CLASS TRTPN POOLSITE;  
MODEL CFB = TRTPN POOLSITE BASE;  
LSMEANS TRTPN / PDIFF CL;  
ESTIMATE 'LINEAR TREND' TRTPN 0 1 -1 /CL;  
ESTIMATE 'DOSE-RESPONSE 20 vs 80-160' TRTPN -1 1 0/CL;  
RUN;
```

3. Sensitivity Analysis

a. Random Effects Pattern Model

```
If TRT01PN=1 then DOSE1=1 else DOSE1=0;  
If TRT01PN=2 then DOSE2=1 else DOSE2=0;  
If COMPLFL="Y" then DROP=1 else DROP=0;
```

```
PROC MIXED;  
CLASS USUBJID;  
MODEL AVAL = QSDAY DOSE1 DOSE2 QSDAY*DOSE1 QSDAY*DOSE2  

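### The primary MMRM fits one baseline-MADRS slope for Weeks 1 to 6; if that slope varies by visit, Week 6 is only partly baseline-adjusted and a little precision is lost

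*SAP*

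**What the plan says.** Three places define the primary model, and they agree.

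- SAP 15.1.3.1 has treatment and visit as factors, then "pooled center, the MADRS total score at baseline as a covariate, and the treatment-by-visit interaction".
- Protocol 9.5.2 has "the MADRS total score at baseline as a covariate, and the treatment-by-visit interaction".
- SAP Appendix 3, item 1, codes it as "MODEL CFB = BASE POOLSITE TRTPN AVISIT TRTPN*AVISIT/DDFM=KR".

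None contains a baseline-by-visit term. On the covariance, the SAP states: "An unstructured covariance matrix will be used for the within-patient correlation".

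The non-convergence fallback and the MMRM run after placebo-based imputation (both in Appendix 3) and the subgroup MMRM (SAP 15.2.4) also enter baseline once. The LOCF ANCOVA (SAP 15.1.4.1) fits a slope to the LOCF endpoint alone.

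The documents give no reason for a constant slope. They give no baseline SD and no slope by visit. SAP 3.3 declares no change from the protocol's analysis.

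**The concern.** The treatment effect may take a different value at each visit, but the baseline effect may not. If change scores depend more strongly on baseline at Week 6 than at Week 1, a common slope cannot fit both. Generalised least squares weights the visits where change varies least. If those are the early ones, the pooled slope settles near the Week 1 value and Week 6, the primary time point, is under-adjusted.

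Two things would follow at Week 6. The residual variance would be larger than it need be, and part of any chance baseline difference between arms would stay in the estimated treatment effect.

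The planning SD matters here too. Protocol 3.5 bases its effect size on an earlier study analysed by endpoint ANCOVA, so the SD of 10 reflects a slope fitted to that endpoint. The MMRM may not fully deliver that adjustment.

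**Working it through.** **Inputs from the documents.** Protocol 3.5 gives "A common effect size of 0.35 (ie, an intergroup difference in change from baseline of 3.5 with a standard deviation of 10". It also says "A sample size of 161 per group for a total of 483 patients was estimated", for "complete power (probability of rejecting 2 null hypotheses) of 80" percent, "with a one-sided 2.5% significance level using Hochberg procedure for multiplicity adjustment". SAP 15.1.4.2 gives dropout of 17.4%.

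**Step 1: the plan's own figure.** Under Hochberg, both nulls are rejected when both two-sided p-values are at most 0.05. Complete power is therefore P(Z1 > 1.96 and Z2 > 1.96), with each mean equal to 0.35 × √(161/2) = 3.14 and correlation 0.5 from the shared placebo arm.

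- The result is 0.804 (0.800 in a t-based simulation), so the stated 80% reproduces.
- Protocol Table 2 implies an SD of 1.10/√(1/161 + 1/162) = 9.9, consistent with the planned 10.

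**Step 2: assumptions, none of them in the documents.**

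- Baseline SD σ_b is 4.5 to 5.5.
- The true slope of change on baseline reaches b6 = -0.3 to -0.5 at Week 6, rising linearly from 30% of that at Week 1.
- Residual SD rises linearly from 5.5 to 10; only the 10 is the protocol's.
- Correlation is AR(0.75 to 0.85) or exchangeable (0.5 to 0.65).
- Data are complete.

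**Step 3: formulas.** Let b be the vector of true slopes and Σ the residual covariance.

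- Fitted common slope: b̄ = (1′V⁻¹b)/(1′V⁻¹1), with V = Σ + σ_b²(b − b̄)(b − b̄)′, iterated to convergence.
- Week 6 variance factor: 1 + (b6 − b̄)²σ_b²/10².
- Shift left by a 1-SE baseline imbalance: |b6 − b̄| × σ_b × √(2/161).
- Complete power: as in Step 1, with 0.35 divided by the square root of the variance factor.

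**Step 4: results.**

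| Case | b̄ | Gap | Variance factor | Shift (points) | Complete power |
|---|---|---|---|---|---|
| σ_b 4.5, b6 -0.3, AR 0.75 | -0.130 | 0.170 | 1.006 | 0.09 | 0.801 |
| σ_b 5, b6 -0.4, AR 0.85 | -0.139 | 0.261 | 1.017 | 0.15 | 0.796 |
| σ_b 5.5, b6 -0.5, exchangeable 0.65 | -0.102 | 0.398 | 1.048 | 0.24 | 0.781 |
| Constant slope | same as b6 | 0 | 1.000 | 0 | 0.804 |

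For the middle row, 1 + 0.261² × 25/100 = 1.017 and 0.261 × 5 × 0.1115 = 0.15. Over the whole grid b̄ lies between -0.06 and -0.22. The variance excess of 0.6% to 4.8% is worth 161 × 0.006 ≈ 1 to 161 × 0.048 ≈ 8 patients per arm. Complete power falls by 0.3 to 2.2 points.

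**Step 5: simulation of the fitted models.** I ran 8,000 replicates with 161 per arm, complete data and no site effect. Residual SD rose from 5 to 10, with AR(0.85) correlation.

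| Baseline SD, slopes | Model | Mean estimate (true -3.5) | Empirical SE | Complete power | Type I error per comparison |
|---|---|---|---|---|---|
| 5, -0.10 to -0.45 | slope by visit | -3.49 | 1.112 | 0.806 | 0.053 |
| | common slope | -3.49 | 1.131 | 0.789 | 0.052 |
| 6, -0.15 to -0.60 | slope by visit | -3.50 | 1.116 | 0.804 | 0.050 |
| | common slope | -3.50 | 1.160 | 0.763 | 0.051 |
| 5, -0.40 throughout | slope by visit | -3.50 | 1.119 | 0.803 | 0.048 |
| | common slope | -3.50 | 1.118 | 0.805 | 0.048 |

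The second pair goes beyond the main range: the SE is 3.9% larger and the power loss is about 4 points. In the large-sample calculation for that setting (baseline SD 6, AR 0.85), adding 17.4% monotone dropout barely changed the SE ratio (1.037 against 1.038).

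**The case against.** The strongest reply is that this is a consistent, prespecified model, and that the loss rests on slopes, a baseline SD and a correlation that the documents do not contain. That stands. The plan contains no error or contradiction here, and the loss is conditional.

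Three stronger readings are tempting, and the documents support none of them.

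- *The primary comparison is biased or its test invalid.* It is not. Baseline is still adjusted for through the common slope. Only the slope gap times the chance imbalance remains, randomisation makes that zero on average, and the unstructured covariance carries its variance into the standard error.
- *The trial has no slack, so any loss sinks it below 80%.* The 28 pooled centres in SAP Table B sum to 524 subjects against a target of 501. That is about 175 per arm, and the protocol's own ratio of 161/167 leaves about 168 analysed. Complete power is then 82.3%, and still about 80% after a 4.8% variance loss. Like the protocol's calculation, this does not model dropout.
- *The LOCF ANCOVA already has the right Week 6 slope.* Its endpoint mixes completers' Week 6 values with earlier values from the 17.4% who dropped out, so its slope belongs to that mixture. It is a partial check only.

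The reply also notes that the SAP was finalised on 30MAR2017, after last patient last visit on 20FEB2017. A change now departs from the protocol-stated primary model and needs a reason. That is a real cost, but Protocol 9.1 provides for it.

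**Conclusion.** The point holds as a cheap gain in precision, conditional on the baseline slope differing between Week 6 and the earlier visits. It is not a validity failure.

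Under the Step 2 assumptions the common slope costs 0.6% to 4.8% in Week 6 variance and 0.3 to 2.2 points of complete power. It leaves 0.09 to 0.24 MADRS points in the difference per standard error of baseline imbalance, which is 2.4% to 7% of the planned 3.5. These power figures take the protocol's SD of 10 as the fully adjusted Week 6 SD. If 10 is instead what the planned model delivers, the planned power stays at 80.4% and the extra term adds a similar amount to it. A larger gap or baseline SD would cost more, and a constant slope would cost nothing.

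The case for acting is the asymmetry. With equal slopes the two models performed alike in simulation; with unequal slopes the extra term recovers precision from data already collected.

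**What to change.** Before unblinding, add `BASE*AVISIT` to the MODEL statement of the primary MMRM. For consistency, add the same term to the non-convergence fallback, the MMRM run on the imputed data and the subgroup MMRM. Amend SAP 15.1.3.1, 15.2.4 and Appendix 3 to match. Replace the statement in SAP 3.3 that nothing has changed with an entry giving this change and its reason.

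If the sponsor prefers to keep the protocol's model as primary, the lesser option is to prespecify the version with the interaction as a sensitivity analysis.

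The cost is 5 degrees of freedom (six slopes instead of one) out of up to 483 × 6 = 2,898 observations, plus a documented departure from the protocol-stated model. No new data are needed. Extending the term to the CGI-BP-S, YMRS and DIEPSS MMRMs is optional; I have not quantified any gain there.
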